## EFFICACY ENDPOINTS

	e-CIG VS. IQOS Statistical Analysis Plan Version 2.0	Doc code: BIOSTAT.SAP.02
		Pag. 42 of 115

Sponsor: Center for Tobacco Research, Cessation and Prevention, [name]  
Protocol: Progetto e-cig vs IQOS

Table E.1a Summary of the Primary End-point. Quit Rate at all visits  
Population: <Per-Protocol/Intention-To-Treat>

			Group HnB N=XXXX	Group EC N=XXXX
Quit rate	Visit 1	N(%)	XXX (XX.X%)	XXX (XX.X%)
	Visit 2	N(%)	XXX (XX.X%)	XXX (XX.X%)
	...	N(%)	XXX (XX.X%)	XXX (XX.X%)
	Visit n	N(%)	XXX (XX.X%)	XXX (XX.X%)

<File: [..]\Work\_In\_Progress\[..]\Statistica\Programmi\xxxxx.sas>

<Source: [..]\Work\_In\_Progress\[..]\Gestione Dati\Dati SAS\xxxxx.sas7bdat>      Generated on XXXXXXXXXX XX:XX

As for the PP population, a "Continuous Quitter" is defined as the subject who did not smoke conventional cigarettes from visit 4 to visit 6

The p-value was derived from the XXXX test

For further information see Listing X.X

Sponsor: Center for Tobacco Research, Cessation and Prevention, [name]  
Protocol: Progetto e-cig vs IQOS

Table E.1b Summary of the Primary End-point. Quit Rate at final visit comparison  
Population: <Per-Protocol/Intention-To-Treat>

		Group HnB N=XXXX	Group EC N=XXXX
Quit Rate	Rate 95%CI	XX.X% [XX.XX,XXX.X]	XX.X% [XX.XX,XXX.X]

H0: P1-P2 ≤ -Margin  
H1: P1-P2 > -Margin

Margin=X.XXX

Score (Farrington-Manning)

Proportion Difference	ASE (F-M)	Z	Pr>Z
X.XXXX	X.XXXX	X.XXXX	X.XXXX

Noninferiority Limit	95% Confedent Limits	
X.XXXX	X.XXXX	X.XXXX

<File: [..]\Work\_In\_Progress\[..]\Statistica\Programmi\xxxxx.sas>

<Source: [..]\Work\_In\_Progress\[..]\Gestione Dati\Dati SAS\xxxxx.sas7bdat>      Generated on XXXXXXXXXX XX:XX

As for the PP population, a "Continuous Quitter" is defined as the subject who did not smoke conventional cigarettes from visit 4 to visit 6  
For further information see Listing X.X

	e-CIG VS. IQOS Statistical Analysis Plan Version 2.0	Doc code: BIOSTAT.SAP.02
		Pag. 44 of 115

Sponsor: Center for Tobacco Research, Cessation and Prevention, [name]  
Protocol: Progetto e-cig vs IQOS

Table E.2a Summary of Smoking Reduction derived from the use of HnB and EC at week 12  
Population: <Per-Protocol/Intention-To-Treat>

		Group HnB	Group EC	p-value
		N=XXXX	N=XXXX	
Smoking Reduction	Rate 95%CI	XX.X% [XX.XX,XXX.X]	XX.X% [XX.XX,XXX.X]	X.XXXX

<File: [..]\Work\_In\_Progress\[..]\Statistica\Programmi\xxxxx.sas>  
<Source: [..]\Work\_In\_Progress\[..]\Gestione Dati\Dati SAS\xxxxx.sas7bdat>      Generated on XXXXXXXXXX XX:XX  
Smoking reduction is intended as a least a 50% reduction in the number of conventional cigarette/day at week 12.  
The p-value was derived from the XXXX test  
For further information see Listing X.X

Sponsor: Center for Tobacco Research, Cessation and Prevention, [name]  
Protocol: Progetto e-cig vs IQOS

Table E.2b Summary of Smoking Reduction derived from the use of HnB and EC according to the Russell Standard Population: <Per-Protocol/Intention-To-Treat>

Quit timepoint		Group HnB	Group EC	p-value
		N=XXX	N=XXX	
Self-reported 4 week	Rate	XX.X%	XX.X%	X.XXXX
	95%CIIs	[XX.XX,XXX.X]	[XX.XX,XXX.X]	
eCO checked* 4 weeks	Rate	XX.X%	XX.X%	X.XXXX
	95%CIIs	[XX.XX,XXX.X]	[XX.XX,XXX.X]	
eCO checked* 12 weeks	Rate	XX.X%	XX.X%	X.XXXX
	95%CIIs	[XX.XX,XXX.X]	[XX.XX,XXX.X]	
eCO checked* 24 weeks	Rate	XX.X%	XX.X%	X.XXXX
	95%CIIs	[XX.XX,XXX.X]	[XX.XX,XXX.X]	
Lost to FU 24 weeks	Rate	XX.X%	XX.X%	X.XXXX
	95%CIIs	[XX.XX,XXX.X]	[XX.XX,XXX.X]	

<File: [..]\Work\_In\_Progress\[..]\Statistica\Programmi\xxxxx.sas>  
<Source: [..]\Work\_In\_Progress\[..]\Gestione Dati\Dati SAS\xxxxx.sas7bdat>      Generated on XXXXXXXXXX XX:XX

\* expired-air 'CO-verified (eCO) 4-week quitter' is the subject that was found to be less than 10ppm in the past 2 weeks  
The p-value was derived from the XXXX test  
For further information see Listing X.X

	e-CIG VS. IQOS Statistical Analysis Plan Version 2.0	Doc code: BIOSTAT.SAP.02
		Pag. 46 of 115

Sponsor: Center for Tobacco Research, Cessation and Prevention, [name]  
Protocol: Progetto e-cig vs IQOS

Table E.3 Summary of Adoption Rate and Adherence to product use at week 12  
Population: <Per-Protocol/Intention-To-Treat>

		Group HnB	Group EC	p-value
		N=XXXX	N=XXXX	
Adoption Rate	Rate 95%CIs	XX.X% [XX.XX, XXX.X]	XX.X% [XX.XX, XXX.X]	X.XXXX

<File: [..]\Work\_In\_Progress\[..]\Statistica\Programmi\xxxxx.sas>  
<Source: [..]\Work\_In\_Progress\[..]\Gestione Dati\Dati SAS\xxxxx.sas7bdat>      Generated on XXXXXXXXXX XX:XX  
A subject is defined as "Compliant" if he/she used at least a 90% of the product  
The p-value was derived from the XXXX test  
For further information see Listing X.X

Sponsor: Center for Tobacco Research, Cessation and Prevention, [name]  
 Protocol: Progetto e-cig vs IQOS

Table E.4a1 Summary of the mCE Questionnaire (scores) by visit < Group HnB / Group EC >  
 Population: <Per-Protocol/Intention-To-Treat>

Parameter	Visit	Observed Values at Visit							Changes From Visit 1 to Visits n						
		N	N miss	Mean	STD	CI 95%	Median	Range (Q1-Q3)	N	N miss	Mean	STD	CI 95%	Median	Range (Q1-Q3)
Satisfaction	Visit 4	XX	XX	XX.XX	XX.XX	[XX.XX,XXX.X]	XX.XX	XX.XX - XXX.X							
	Visit 5	XX	XX	XX.XX	XX.XX	[XX.XX,XXX.X]	XX.XX	XX.XX - XXX.X							
	Visit 6	XX	XX	XX.XX	XX.XX	[XX.XX,XXX.X]	XX.XX	XX.XX - XXX.X							
	Visit 7	XX	XX	XX.XX	XX.XX	[XX.XX,XXX.X]	XX.XX	XX.XX - XXX.X	XX	XX	XX.XX	XX.XX	[XX.XX,XXX.X]	XX.XX	XX.XX - XXX.X
Psychological Reward	Visit 4	XX	XX	XX.XX	XX.XX	[XX.XX,XXX.X]	XX.XX	XX.XX - XXX.X							
	Visit 5	XX	XX	XX.XX	XX.XX	[XX.XX,XXX.X]	XX.XX	XX.XX - XXX.X							
	Visit 6	XX	XX	XX.XX	XX.XX	[XX.XX,XXX.X]	XX.XX	XX.XX - XXX.X							
	Visit 7	XX	XX	XX.XX	XX.XX	[XX.XX,XXX.X]	XX.XX	XX.XX - XXX.X	XX	XX	XX.XX	XX.XX	[XX.XX,XXX.X]	XX.XX	XX.XX - XXX.X
Aversion	Visit 4	XX	XX	XX.XX	XX.XX	[XX.XX,XXX.X]	XX.XX	XX.XX - XXX.X							
	Visit 5	XX	XX	XX.XX	XX.XX	[XX.XX,XXX.X]	XX.XX	XX.XX - XXX.X							
	Visit 6	XX	XX	XX.XX	XX.XX	[XX.XX,XXX.X]	XX.XX	XX.XX - XXX.X							
	Visit 7	XX	XX	XX.XX	XX.XX	[XX.XX,XXX.X]	XX.XX	XX.XX - XXX.X	XX	XX	XX.XX	XX.XX	[XX.XX,XXX.X]	XX.XX	XX.XX - XXX.X
Enjoyment of Sensation	Visit 4	XX	XX	XX.XX	XX.XX	[XX.XX,XXX.X]	XX.XX	XX.XX - XXX.X							
	Visit 5	XX	XX	XX.XX	XX.XX	[XX.XX,XXX.X]	XX.XX	XX.XX - XXX.X							
	Visit 6	XX	XX	XX.XX	XX.XX	[XX.XX,XXX.X]	XX.XX	XX.XX - XXX.X							
	Visit 7	XX	XX	XX.XX	XX.XX	[XX.XX,XXX.X]	XX.XX	XX.XX - XXX.X	XX	XX	XX.XX	XX.XX	[XX.XX,XXX.X]	XX.XX	XX.XX - XXX.X
Craving Reduction	Visit 4	XX	XX	XX.XX	XX.XX	[XX.XX,XXX.X]	XX.XX	XX.XX - XXX.X							
	Visit 5	XX	XX	XX.XX	XX.XX	[XX.XX,XXX.X]	XX.XX	XX.XX - XXX.X							
	Visit 6	XX	XX	XX.XX	XX.XX	[XX.XX,XXX.X]	XX.XX	XX.XX - XXX.X							
	Visit 7	XX	XX	XX.XX	XX.XX	[XX.XX,XXX.X]	XX.XX	XX.XX - XXX.X	XX	XX	XX.XX	XX.XX	[XX.XX,XXX.X]	XX.XX	XX.XX - XXX.X
TOTAL	Visit 4	XX	XX	XX.XX	XX.XX	[XX.XX,XXX.X]	XX.XX	XX.XX - XXX.X							
	Visit 5	XX	XX	XX.XX	XX.XX	[XX.XX,XXX.X]	XX.XX	XX.XX - XXX.X							
	Visit 6	XX	XX	XX.XX	XX.XX	[XX.XX,XXX.X]	XX.XX	XX.XX - XXX.X							
	Visit 7	XX	XX	XX.XX	XX.XX	[XX.XX,XXX.X]	XX.XX	XX.XX - XXX.X	XX	XX	XX.XX	XX.XX	[XX.XX,XXX.X]	XX.XX	XX.XX - XXX.X

Sponsor: Center for Tobacco Research, Cessation and Prevention, [name]  
Protocol: Progetto e-cig vs IQOS

Table E.4a2 mCE Questionnaire (scores). Inferential analysis on the mean changes at final visit from baseline  
Population: <Per-Protocol/Intention-To-Treat>

		Group HnB N=XXXX	Group EC N=XXXX	p-value
Satisfaction	Mean	XX.X	XX.X	X.XXXX
Psychological Reward	Mean	XX.X	XX.X	X.XXXX
Aversion	Mean	XX.X	XX.X	X.XXXX
Enjoyment of Sensation	Mean	XX.X	XX.X	X.XXXX
Craving Reduction	Mean	XX.X	XX.X	X.XXXX
TOTAL	Mean	XX.X	XX.X	X.XXXX

Sponsor: Center for Tobacco Research, Cessation and Prevention, [name]  
Protocol: Progetto e-cig vs IQOS

Table E.4b1 Summary of Smoking Cue Appeal Questionnaire by visit. <Question 1 of 8>  
Population: <Per-Protocol/Intention-To-Treat>

<Question>

Visit	Score	Group HnB	Group EC
Visit 4	1	XX (XX.X%)	XX (XX.X)
	2	XX (XX.X%)	XX (XX.X)
	3	XX (XX.X%)	XX (XX.X)
	4	XX (XX.X%)	XX (XX.X)
	5	XX (XX.X%)	XX (XX.X)
	6	XX (XX.X%)	XX (XX.X)
	7	XX (XX.X%)	XX (XX.X)
Visit 5	1	XX (XX.X%)	XX (XX.X)
	2	XX (XX.X%)	XX (XX.X)
	3	XX (XX.X%)	XX (XX.X)
	4	XX (XX.X%)	XX (XX.X)
	5	XX (XX.X%)	XX (XX.X)
	6	XX (XX.X%)	XX (XX.X)
	7	XX (XX.X%)	XX (XX.X)
Visit 6	1	XX (XX.X%)	XX (XX.X)
	2	XX (XX.X%)	XX (XX.X)
	3	XX (XX.X%)	XX (XX.X)
	4	XX (XX.X%)	XX (XX.X)
	5	XX (XX.X%)	XX (XX.X)
	6	XX (XX.X%)	XX (XX.X)
	7	XX (XX.X%)	XX (XX.X)
Visit 7	1	XX (XX.X%)	XX (XX.X)
	2	XX (XX.X%)	XX (XX.X)
	3	XX (XX.X%)	XX (XX.X)
	4	XX (XX.X%)	XX (XX.X)
	5	XX (XX.X%)	XX (XX.X)
	6	XX (XX.X%)	XX (XX.X)
	7	XX (XX.X%)	XX (XX.X)

<File: [..]\Work\_In\_Progress\[..]\Statistica\Programmi\xxxxx.sas>

<Source: [..]\Work\_In\_Progress\[..]\Gestione Dati\Dati SAS\xxxxx.satd7sas> Generated on XXXXXXXX XX:XX

Legend: 1. Estremamente sgradevole ; 2. Molto sgradevole ; 3. Sgradevole ; 4. Né piacevole, né sgradevole ; 5. Piacevole  
6. Molto piacevole ; 7. Estremamente piacevole

For further information see Listing X.X

	e-CIG VS. IQOS Statistical Analysis Plan Version 2.0	Doc code: BIOSTAT.SAP.02
		Pag. 50 of 115

Sponsor: Center for Tobacco Research, Cessation and Prevention, [name]  
Protocol: Progetto e-cig vs IQOS

Table E.4b2 Smoking Cue Appeal Questionnaire. Inferential analysis on the mean changes at final visit from baseline  
Population: <Per-Protocol/Intention-To-Treat>

		Group HnB N=XXXX	Group EC N=XXXX	p-value
Question 1	Mean	XX.X	XX.X	X.XXXX
Question 2	Mean	XX.X	XX.X	X.XXXX
...	Mean	XX.X	XX.X	X.XXXX
Question 8	Mean	XX.X	XX.X	X.XXXX
TOTAL	Mean	XX.X	XX.X	X.XXXX

<File: [..]\Work\_In\_Progress\[..]\Statistica\Programmi\xxxxx.sas>  
<Source: [..]\Work\_In\_Progress\[..]\Gestione Dati\Dati SAS\xxxxx.sas7bdat>      Generated on XXXXXXXXXX XX:XX  
For the inferential analysis, the scores were considered as numbers.  
The p-value was derived from the XXXX test  
For further information see Listing X.X

Sponsor: Center for Tobacco Research, Cessation and Prevention, [name]  
Protocol: Progetto e-cig vs IQOS

Table E.4c1 Summary of the ITU Questionnaire by visit. <Question 4 (of questions 4-5-6)>  
Population: <Per-Protocol/Intention-To-Treat>

<Question>

Visit	Score	Group HnB	Group EC
Visit 4	1	XX (XX.X%)	XX (XX.X)
	2	XX (XX.X%)	XX (XX.X)
	3	XX (XX.X%)	XX (XX.X)
	4	XX (XX.X%)	XX (XX.X)
	5	XX (XX.X%)	XX (XX.X)
	6	XX (XX.X%)	XX (XX.X)
	7	XX (XX.X%)	XX (XX.X)
Visit 5	1	XX (XX.X%)	XX (XX.X)
	2	XX (XX.X%)	XX (XX.X)
	3	XX (XX.X%)	XX (XX.X)
	4	XX (XX.X%)	XX (XX.X)
	5	XX (XX.X%)	XX (XX.X)
	6	XX (XX.X%)	XX (XX.X)
	7	XX (XX.X%)	XX (XX.X)
Visit 6	1	XX (XX.X%)	XX (XX.X)
	2	XX (XX.X%)	XX (XX.X)
	3	XX (XX.X%)	XX (XX.X)
	4	XX (XX.X%)	XX (XX.X)
	5	XX (XX.X%)	XX (XX.X)
	6	XX (XX.X%)	XX (XX.X)
	7	XX (XX.X%)	XX (XX.X)
Visit 7	1	XX (XX.X%)	XX (XX.X)
	2	XX (XX.X%)	XX (XX.X)
	3	XX (XX.X%)	XX (XX.X)
	4	XX (XX.X%)	XX (XX.X)
	5	XX (XX.X%)	XX (XX.X)
	6	XX (XX.X%)	XX (XX.X)
	7	XX (XX.X%)	XX (XX.X)

<File: [..]\Work\_In\_Progress\[..]\Statistica\Programmi\xxxxx.sas>

<Source: [..]\Work\_In\_Progress\[..]\Gestione Dati\Dati SAS\xxxxx.satd7sas> Generated on XXXXXXXX XX:XX

Legend: 1. Assolutamente falso ; 2. Falso ; 3. Piuttosto falso ; 4. Piuttosto vero ; 5. Vero ; 6. Molto vero ; 7. Verissimo

For further information see Listing X.X

Sponsor: Center for Tobacco Research, Cessation and Prevention, [name]  
Protocol: Progetto e-cig vs IQOS

Table E.4c2 ITU Questionnaire. Inferential analysis on the mean changes at final visit from baseline  
Population: <Per-Protocol/Intention-To-Treat>

		Group HnB N=XXXX	Group EC N=XXXX	p-value
Question 4	Mean	XX.X	XX.X	X.XXXX
Question 5	Mean	XX.X	XX.X	X.XXXX
Question 6	Mean	XX.X	XX.X	X.XXXX
TOTAL	Mean	XX.X	XX.X	X.XXXX

Sponsor: Center for Tobacco Research, Cessation and Prevention, [name]  
Protocol: Progetto e-cig vs IQOS

Table E.4d1 Summary of the Risk Perception (PRI-P CC) Questionnaire by visit. <Question 1 of 18>  
Population: <Per-Protocol/Intention-To-Treat>

<Question>

Visit	Score	Group HnB	Group EC
Visit 4	1	XX (XX.X%)	XX (XX.X)
	2	XX (XX.X%)	XX (XX.X)
	3	XX (XX.X%)	XX (XX.X)
	4	XX (XX.X%)	XX (XX.X)
	5	XX (XX.X%)	XX (XX.X)
	6	XX (XX.X%)	XX (XX.X)
Visit 5	1	XX (XX.X%)	XX (XX.X)
	2	XX (XX.X%)	XX (XX.X)
	3	XX (XX.X%)	XX (XX.X)
	4	XX (XX.X%)	XX (XX.X)
	5	XX (XX.X%)	XX (XX.X)
	6	XX (XX.X%)	XX (XX.X)
Visit 6	1	XX (XX.X%)	XX (XX.X)
	2	XX (XX.X%)	XX (XX.X)
	3	XX (XX.X%)	XX (XX.X)
	4	XX (XX.X%)	XX (XX.X)
	5	XX (XX.X%)	XX (XX.X)
	6	XX (XX.X%)	XX (XX.X)
Visit 7	1	XX (XX.X%)	XX (XX.X)
	2	XX (XX.X%)	XX (XX.X)
	3	XX (XX.X%)	XX (XX.X)
	4	XX (XX.X%)	XX (XX.X)
	5	XX (XX.X%)	XX (XX.X)
	6	XX (XX.X%)	XX (XX.X)

<File: [..]\Work\_In\_Progress\[..]\Statistica\Programmi\xxxxx.sas>

<Source: [..]\Work\_In\_Progress\[..]\Gestione Dati\Dati SAS\xxxxx.satd7sas> Generated on XXXXXXXXXX XX:XX

Legend: 1. Nessun rischio ; 2. Rischio basso ; 3. Rischio moderato ; 4. Rischio alto ; 5. Rischio molto alto ; 6. Non so

For further information see Listing X.X

Sponsor: Center for Tobacco Research, Cessation and Prevention, [name]  
Protocol: Progetto e-cig vs IQOS

Table E.4d2 Risk Perception (PRI-P CC) Questionnaire. Inferential analysis on the mean changes at final visit from baseline

		Group HnB N=XXXX	Group EC N=XXXX	p-value
Question 1	Mean	XX.X	XX.X	X.XXXX
Question 2	Mean	XX.X	XX.X	X.XXXX
...	Mean	XX.X	XX.X	X.XXXX
Question 18	Mean	XX.X	XX.X	X.XXXX
TOTAL	Mean	XX.X	XX.X	X.XXXX

---

<File: [..]\Work\_In\_Progress\[..]\Statistica\Programmi\xxxxx.sas>  
<Source: [..]\Work\_In\_Progress\[..]\Gestione Dati\Dati SAS\xxxxx.sas7bdat>      Generated on XXXXXXXXXX XX:XX  
For the inferential analysis, the scores were considered as numbers. Score 6 was not included.  
The p-value was derived from the XXXX test  
For further information see Listing X.X

Sponsor: Center for Tobacco Research, Cessation and Prevention, [name]  
Protocol: Progetto e-cig vs IQOS

Table E.4e1 Summary of the Risk Perception (PRI-P RRP) Questionnaire by visit. <Question 1 of 18>  
Population: <Per-Protocol/Intention-To-Treat>

<Question>

Visit	Score	Group HnB	Group EC
Visit 4	1	XX (XX.X%)	XX (XX.X)
	2	XX (XX.X%)	XX (XX.X)
	3	XX (XX.X%)	XX (XX.X)
	4	XX (XX.X%)	XX (XX.X)
	5	XX (XX.X%)	XX (XX.X)
	6	XX (XX.X%)	XX (XX.X)
Visit 5	1	XX (XX.X%)	XX (XX.X)
	2	XX (XX.X%)	XX (XX.X)
	3	XX (XX.X%)	XX (XX.X)
	4	XX (XX.X%)	XX (XX.X)
	5	XX (XX.X%)	XX (XX.X)
	6	XX (XX.X%)	XX (XX.X)
Visit 6	1	XX (XX.X%)	XX (XX.X)
	2	XX (XX.X%)	XX (XX.X)
	3	XX (XX.X%)	XX (XX.X)
	4	XX (XX.X%)	XX (XX.X)
	5	XX (XX.X%)	XX (XX.X)
	6	XX (XX.X%)	XX (XX.X)
Visit 7	1	XX (XX.X%)	XX (XX.X)
	2	XX (XX.X%)	XX (XX.X)
	3	XX (XX.X%)	XX (XX.X)
	4	XX (XX.X%)	XX (XX.X)
	5	XX (XX.X%)	XX (XX.X)
	6	XX (XX.X%)	XX (XX.X)

<File: [..]\Work\_In\_Progress\[..]\Statistica\Programmi\xxxxx.sas>

<Source: [..]\Work\_In\_Progress\[..]\Gestione Dati\Dati SAS\xxxxx.satd7sas> Generated on XXXXXXXXXX XX:XX

Legend: 1. Nessun rischio ; 2. Rischio basso ; 3. Rischio moderato ; 4. Rischio alto ; 5. Rischio molto alto ; 6. Non so

For further information see Listing X.X

Sponsor: Center for Tobacco Research, Cessation and Prevention, [name]  
Protocol: Progetto e-cig vs IQOS

Table E.4e2 Risk Perception (PRI-P RRP) Questionnaire. Inferential analysis on the mean changes at final visit from baseline  
Population: <Per-Protocol/Intention-To-Treat>

		Group HnB N=XXXX	Group EC N=XXXX	p-value
Question 1	Mean	XX.X	XX.X	X.XXXX
Question 2	Mean	XX.X	XX.X	X.XXXX
...	Mean	XX.X	XX.X	X.XXXX
Question 18	Mean	XX.X	XX.X	X.XXXX
TOTAL	Mean	XX.X	XX.X	X.XXXX

---

<File: [..]\Work\_In\_Progress\[..]\Statistica\Programmi\xxxxx.sas>  
<Source: [..]\Work\_In\_Progress\[..]\Gestione Dati\Dati SAS\xxxxx.sas7bdat>      Generated on XXXXXXXXXX XX:XX  
For the inferential analysis, the scores were considered as numbers. Score 6 was not included.  
The p-value was derived from the XXXX test  
For further information see Listing X.X

Sponsor: Center for Tobacco Research, Cessation and Prevention, [name]  
Protocol: Progetto e-cig vs IQOS

Table E.4f Summary of Device Delivery by group  
Population: <Per-Protocol/Intention-To-Treat>

		Group HnB	Group EC
		N=XXXX	N=XXXX
Preferred flavor of chopstick chosen	Heets Amber	XX (XX.X%)	XX (XX.X%)
	Heets Yellow	XX (XX.X%)	XX (XX.X%)
	Heets Turquoise	XX (XX.X%)	XX (XX.X%)
Has the devices been tested and does it works?	Yes	XX (XX.X%)	XX (XX.X%)
	No	XX (XX.X%)	XX (XX.X%)
Has the subject been trained for the allocated device?	Yes	XX (XX.X%)	XX (XX.X%)
	No	XX (XX.X%)	XX (XX.X%)

Sponsor: Center for Tobacco Research, Cessation and Prevention, [name]  
Protocol: Progetto e-cig vs IQOS

Table E.5 Summary of the Biomarkers of Biological Exposure (BoBE) - eCO (ppm)  
Population: <Per-Protocol/Intention-To-Treat>

	Visit	Observed Values at Visit						Changes From Visit 1 to Visits n							
		N	N miss	Mean	STD	CI 95%	Median	Range (Q1-Q3)	N	N miss	Mean	STD	CI 95%	Median	Range (Q1-Q3)
Group HnB	Screening	XX	XX	XX.XX	XX.XX	[XX.XX,XXX.X]	XX.XX	(XX.XX - XXX.X)							
	Visit 1	XX	XX	XX.XX	XX.XX	[XX.XX,XXX.X]	XX.XX	(XX.XX - XXX.X)							
	Visit 2	XX	XX	XX.XX	XX.XX	[XX.XX,XXX.X]	XX.XX	(XX.XX - XXX.X)							
	Visit 3	XX	XX	XX.XX	XX.XX	[XX.XX,XXX.X]	XX.XX	(XX.XX - XXX.X)							
	Visit 4	XX	XX	XX.XX	XX.XX	[XX.XX,XXX.X]	XX.XX	(XX.XX - XXX.X)							
	Visit 5	XX	XX	XX.XX	XX.XX	[XX.XX,XXX.X]	XX.XX	(XX.XX - XXX.X)							
	Visit 6	XX	XX	XX.XX	XX.XX	[XX.XX,XXX.X]	XX.XX	(XX.XX - XXX.X)							
	Follow-up	XX	XX	XX.XX	XX.XX	[XX.XX,XXX.X]	XX.XX	(XX.XX - XXX.X)	XX	XX	XX.XX	XX.XX	[XX.XX,XXX.X]	XX.XX	(XX.XX - XXX.X)
Group EC	Screening	XX	XX	XX.XX	XX.XX	[XX.XX,XXX.X]	XX.XX	(XX.XX - XXX.X)							
	Visit 1	XX	XX	XX.XX	XX.XX	[XX.XX,XXX.X]	XX.XX	(XX.XX - XXX.X)							
	Visit 2	XX	XX	XX.XX	XX.XX	[XX.XX,XXX.X]	XX.XX	(XX.XX - XXX.X)							
	Visit 3	XX	XX	XX.XX	XX.XX	[XX.XX,XXX.X]	XX.XX	(XX.XX - XXX.X)							
	Visit 4	XX	XX	XX.XX	XX.XX	[XX.XX,XXX.X]	XX.XX	(XX.XX - XXX.X)							
	Visit 5	XX	XX	XX.XX	XX.XX	[XX.XX,XXX.X]	XX.XX	(XX.XX - XXX.X)							
	Visit 6	XX	XX	XX.XX	XX.XX	[XX.XX,XXX.X]	XX.XX	(XX.XX - XXX.X)							
	Follow-up	XX	XX	XX.XX	XX.XX	[XX.XX,XXX.X]	XX.XX	(XX.XX - XXX.X)	XX	XX	XX.XX	XX.XX	[XX.XX,XXX.X]	XX.XX	(XX.XX - XXX.X)

p-value=X.XXXX

e-CIG VS. IQOS  
Statistical Analysis Plan  
Version 2.0

Doc code:  
BIOSTAT.SAP.02

Pag. 59 of 115

Sponsor: Center for Tobacco Research, Cessation and Prevention, [name]  
Protocol: Progetto e-cig vs IQOS

Table E.6 Summary of EQ-5D Questionnaire (scores). < Group HnB / Group EC >  
Population: <Per-Protocol/Intention-To-Treat/Continuous Quitters>

Parameter	Visit	Observed Values at Visit							Changes From Visit 1 to Visits n						
		N	N miss	Mean	STD	CI 95%	Median	min-max	N	N miss	Mean	STD	CI 95%	Median	min-max
Mobility (1-5)	Visit 1	XX	XX	XX.X	XX.X	[X.X , X.X]	XX.X	(X - X)							
	Visit 4	XX	XX	XX.X	XX.X	[X.X , X.X]	XX.X	(X - X)							
	Visit 5	XX	XX	XX.X	XX.X	[X.X , X.X]	XX.X	(X - X)							
	Visit 6	XX	XX	XX.X	XX.X	[X.X , X.X]	XX.X	(X - X)							
	Visit 7	XX	XX	XX.X	XX.X	[X.X , X.X]	XX.X	(X - X)	XX	XX	XX.X	XX.X	[X.X , X.X]	XX.X	(X - X)
Self-care (1-5)	Visit 1	XX	XX	XX.X	XX.X	[X.X , X.X]	XX.X	(X - X)							
	Visit 4	XX	XX	XX.X	XX.X	[X.X , X.X]	XX.X	(X - X)							
	Visit 5	XX	XX	XX.X	XX.X	[X.X , X.X]	XX.X	(X - X)							
	Visit 6	XX	XX	XX.X	XX.X	[X.X , X.X]	XX.X	(X - X)							
	Visit 7	XX	XX	XX.X	XX.X	[X.X , X.X]	XX.X	(X - X)	XX	XX	XX.X	XX.X	[X.X , X.X]	XX.X	(X - X)
.....															
Health-today (0-100)	Visit 1	XX	XX	XX.X	XX.X	[X.X , X.X]	XX.X	(X - X)							
	Visit 4	XX	XX	XX.X	XX.X	[X.X , X.X]	XX.X	(X - X)							
	Visit 5	XX	XX	XX.X	XX.X	[X.X , X.X]	XX.X	(X - X)							
	Visit 6	XX	XX	XX.X	XX.X	[X.X , X.X]	XX.X	(X - X)							
	Visit 7	XX	XX	XX.X	XX.X	[X.X , X.X]	XX.X	(X - X)	XX	XX	XX.X	XX.X	[X.X , X.X]	XX.X	(X - X)

<File: [..]\Work\_In\_Progress\[..\]Statistica\Programmi\xxxxx.sas>

<Source: [..]\Work\_In\_Progress\[..\]Gestione Dati\Dati SAS\xxxxx.sas7bdat>

Generated on XXXXXXXX XX:XX

For further information see Listing X.X

e-CIG VS. IQOS  
Statistical Analysis Plan  
Version 2.0

Doc code:  
BIOSTAT.SAP.02

Pag. 60 of 115

Sponsor: Center for Tobacco Research, Cessation and Prevention, [name]  
Protocol: Progetto e-cig vs IQOS

Table E.7a Summary of Step Test by group < Group HnB / Group EC >  
Population: <Per-Protocol/Intention-To-Treat>

Parameter	Visit	Observed Values at Visit						Changes From Visit 1 to Visit 7							
		N	N miss	Mean	STD	CI 95%	Median	Range (Q1-Q3)	N	N miss	Mean	STD	CI 95%	Median	Range (Q1-Q3)
Baseline HR	Visit 1	XX	XX	XX.XX	XX.XX	[XX.XX,XXX.X]	XX.XX	(XX.XX - XXX.X)							
	Visit 4	XX	XX	XX.XX	XX.XX	[XX.XX,XXX.X]	XX.XX	(XX.XX - XXX.X)							
	Visit 6	XX	XX	XX.XX	XX.XX	[XX.XX,XXX.X]	XX.XX	(XX.XX - XXX.X)							
	Visit 7	XX	XX	XX.XX	XX.XX	[XX.XX,XXX.X]	XX.XX	(XX.XX - XXX.X)	XX	XX	XX.XX	XX.XX	[XX.XX,XXX.X]	XX.XX	(XX.XX - XXX.X)
SpO2	Visit 1	XX	XX	XX.XX	XX.XX	[XX.XX,XXX.X]	XX.XX	(XX.XX - XXX.X)							
	Visit 4	XX	XX	XX.XX	XX.XX	[XX.XX,XXX.X]	XX.XX	(XX.XX - XXX.X)							
	Visit 6	XX	XX	XX.XX	XX.XX	[XX.XX,XXX.X]	XX.XX	(XX.XX - XXX.X)							
	Visit 7	XX	XX	XX.XX	XX.XX	[XX.XX,XXX.X]	XX.XX	(XX.XX - XXX.X)	XX	XX	XX.XX	XX.XX	[XX.XX,XXX.X]	XX.XX	(XX.XX - XXX.X)
Step 1 HR	Visit 1	XX	XX	XX.XX	XX.XX	[XX.XX,XXX.X]	XX.XX	(XX.XX - XXX.X)							
	Visit 4	XX	XX	XX.XX	XX.XX	[XX.XX,XXX.X]	XX.XX	(XX.XX - XXX.X)							
	Visit 6	XX	XX	XX.XX	XX.XX	[XX.XX,XXX.X]	XX.XX	(XX.XX - XXX.X)							
	Visit 7	XX	XX	XX.XX	XX.XX	[XX.XX,XXX.X]	XX.XX	(XX.XX - XXX.X)	XX	XX	XX.XX	XX.XX	[XX.XX,XXX.X]	XX.XX	(XX.XX - XXX.X)
SpO2	Visit 1	XX	XX	XX.XX	XX.XX	[XX.XX,XXX.X]	XX.XX	(XX.XX - XXX.X)							
	Visit 4	XX	XX	XX.XX	XX.XX	[XX.XX,XXX.X]	XX.XX	(XX.XX - XXX.X)							
	Visit 6	XX	XX	XX.XX	XX.XX	[XX.XX,XXX.X]	XX.XX	(XX.XX - XXX.X)							
	Visit 7	XX	XX	XX.XX	XX.XX	[XX.XX,XXX.X]	XX.XX	(XX.XX - XXX.X)	XX	XX	XX.XX	XX.XX	[XX.XX,XXX.X]	XX.XX	(XX.XX - XXX.X)
...															
Recovery HR	Visit 1	XX	XX	XX.XX	XX.XX	[XX.XX,XXX.X]	XX.XX	(XX.XX - XXX.X)							
	Visit 4	XX	XX	XX.XX	XX.XX	[XX.XX,XXX.X]	XX.XX	(XX.XX - XXX.X)							
	Visit 6	XX	XX	XX.XX	XX.XX	[XX.XX,XXX.X]	XX.XX	(XX.XX - XXX.X)							
	Visit 7	XX	XX	XX.XX	XX.XX	[XX.XX,XXX.X]	XX.XX	(XX.XX - XXX.X)	XX	XX	XX.XX	XX.XX	[XX.XX,XXX.X]	XX.XX	(XX.XX - XXX.X)
SpO2	Visit 1	XX	XX	XX.XX	XX.XX	[XX.XX,XXX.X]	XX.XX	(XX.XX - XXX.X)							
	Visit 4	XX	XX	XX.XX	XX.XX	[XX.XX,XXX.X]	XX.XX	(XX.XX - XXX.X)							
	Visit 6	XX	XX	XX.XX	XX.XX	[XX.XX,XXX.X]	XX.XX	(XX.XX - XXX.X)							
	Visit 7	XX	XX	XX.XX	XX.XX	[XX.XX,XXX.X]	XX.XX	(XX.XX - XXX.X)	XX	XX	XX.XX	XX.XX	[XX.XX,XXX.X]	XX.XX	(XX.XX - XXX.X)

<File: [..]\Work\_In\_Progress\[..]\Statistica\Programmi\xxxxx.sas>  
 <Source: [..]\Work\_In\_Progress\[..]\Gestione Dati\Dati SAS\xxxxx.satd7sas> Generated on XXXXXXXX XX:XX  
 The percentages are calculated on the total of the enrolled patients by group  
 For further information see Listing X.X

Sponsor: Center for Tobacco Research, Cessation and Prevention, [name]  
Protocol: Progetto e-cig vs IQOS

Table E.7b Summary of Step Test - inferential analysis of VO2MAX  
Population: <Per-Protocol/Intention-To-Treat>

		Group HnB	Group EC
VO2MAX	N	XX	XX
	N missing	XX	XX
	Mean	XX.X	XX.X
	Std. deviation	XX.X	XX.X
	Median	XX.X	XX.X
	Q1-Q3	X.X - XX.X	X.X - XX.X
p-value=X.XXXX			

---

<File: [..]\Work\_In\_Progress\[..]\Statistica\Programmi\xxxxx.sas>  
<Source: [..]\Work\_In\_Progress\[..]\Gestione Dati\Dati SAS\xxxxx.satd7sas> Generated on XXXXXXXX XX:XX  
The p-values was derived from the t-test  
For further information see Listing X

	e-CIG VS. IQOS Statistical Analysis Plan Version 2.0	Doc code: BIOSTAT.SAP.02
		Pag. 62 of 115

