## **Statistical Analysis Plan**

### **Sample size calculation**

We assume that:

- current e-vapor products provide a 25% quitting rate in clinical trials (1,2)
- non-inferiority in quit rates means that the proportion of subjects successfully quitting smoking using the test product is not worse than the proportion of subjects quitting smoking using the alternative or reference product, this difference is allowed a tolerance of 15% (3,4).

For sample size definition, we used the Farrington-Manning Score Test for Proportion Difference, assuming:

- asymptotic normal distribution, upper one-tailed
- alpha 0.05
- nominal power 0.80

Thus:

- Null Proportion Diff. -0.15
- Ref Proportion 0.25
- N per group: 104

Consequently, a total of 220 smokers not intending to quit (110 per each arm) will be recruited.

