### **Statistics**

#### **Primary study endpoint:**

Quit rate at 3 months in the experimental (study) group – with respect to reference group – by means a non-inferiority threshold of 15%.

Quit rates will be evaluated on an intention-to-treat basis: subjects known to have failed will be considered as treatment failures in the primary analysis along with subjects lost to follow-up.

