## 3 SAMPLE SIZE

	e-CIG VS. IQOS Statistical Analysis Plan Version 2.0	Doc code: BIOSTAT.SAP.02
		Pag. 9 of 115

Sample size determination (better detailed in the study protocol) for no-inferiority testing is based on the assumptions that:

- 1) expected quit rates based on most recent EC literature is about 20-25% and
- 2) that differences in quit rates between products under investigation should not exceed 10-15% (as per non-inferiority definition).

For sample size definition, Farrington-Manning Score Test for Proportion Difference was used, assuming:

- asymptotic normal distribution, upper one-tailed
- alpha 0.05
- nominal power 0.80

Thus:

- Null Proportion Diff. -0.15
- Ref Proportion 0.25
- N per group: 104

According to these hypotheses the required number of participants per study arm was 104. Hence 220 participants, 110 per group, had to be included.

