## 5 GENERAL INFORMATION FOR THE ANALYSES

	
e-CIG VS. IQOS Statistical Analysis Plan Version 2.0
	Doc code: BIOSTAT.SAP.02
		Pag. 10 of 115

According to the study protocol the statistical analysis will be descriptive in nature.

All the data will be described using standard descriptive statistics, i.e. n, missing, mean, standard deviation, (25th, 50th, 75th) percentiles for numerical variables. As for the categorical variables, frequency tables with count and percentage will be used. In the core of the Statistical Report, the continuous variables will be presented as mean values  $\pm$  standard deviation (SD) or median value and interquartile range [IQR], and categorical variables as numbers and percentages. The descriptive analyses will be presented by group. As indicated in the study protocol, for the primary endpoint, the quit rate at 3 months in the experimental study group will be calculated with a non-inferiority threshold of 15%. The quit rates will be evaluated on an intention-to-treat basis: subjects known to have failed will be considered as treatment failures in the primary analysis along with subjects lost to follow-up.

All the analyses will be performed using SAS® Vers. 9.4.

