# 7 STATISTICAL ANALYSES OF THE EFFICACY ENDPOINTS

The analyses of the primary and secondary endpoints will be carried out of both the ITT and PP populations. Moreover, as for the Step Test and the Quality of Life (i.e. EQ-5D), a further analysis in the subpopulation of the "Continuous Quitter" will be presented.

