## 7.1 Analysis of primary endpoint

The primary endpoint aims to compare the efficacy of HnB and EC in terms of quit rates at week 12 by means a non-inferiority threshold of 15%.

A "Continuous Quitter" is defined as a subject who has a number of conventional cigarette/day equal to zero from Visit 4 to Visit 6. The Farrington-Manning Score Test for Proportion Difference will be used for comparing the quit rates of the two groups. The SAS® PROC FREQ with the METHOD=FM option will be used. The quit rates of the two groups, along with the relevant 95% Confidence Intervals, will be summarized in Table E.1 (Appendix 2).

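### Table E.1b sets 95% limits for the difference beside the noninferiority limit, the trial is sized at one-sided 0.05 (a 90% interval), and SAP 7.1 does not say which criterion decides

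*SAP*

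**What the plan says.** The sample-size sections of both documents (Protocol, Sample size calculation; SAP section 3) specify a Farrington-Manning test, "asymptotic normal distribution, upper one-tailed", with alpha 0.05, power 0.80, null difference -0.15, reference rate 0.25 and 104 per group, raised to 110. On the margin the protocol says "this difference is allowed a tolerance of 15"%.

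SAP 7.1 repeats the 15% threshold and says: "The Farrington-Manning Score Test for Proportion Difference will be used for comparing the quit rates of the two groups". It gives no significance level and no condition for concluding non-inferiority. The only intervals it mentions are for the rates themselves: "The quit rates of the two groups, along with the relevant 95% Confidence Intervals, will be summarized in Table E.1 (Appendix 2".

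An interval for the difference appears only in the shell of Table E.1b. The shell shows one-sided H0 and H1, the Farrington-Manning Z, a one-sided Pr>Z with no cut-off, and then the noninferiority limit beside "95% Confedent Limits".

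The protocol's primary-endpoint section says "Quit rates will be evaluated on an intention-to-treat basis", and SAP section 5 repeats it. SAP section 7 then says: "The analyses of the primary and secondary endpoints will be carried out of both the ITT and PP populations". Table E.1b is therefore produced for each population.

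**The concern.** A one-sided test at 0.05 corresponds to the lower limit of a two-sided 90% interval. The lower limit of a two-sided 95% interval is a one-sided 0.025 criterion. An interval printed next to the margin invites comparison with it, and here that comparison is not the test the trial was sized for. When the one-sided p-value lies between 0.025 and 0.05, the primary table would show a p-value that passes at the sized level and a lower limit beyond -0.15. A reader could draw either conclusion. With no written rule, the choice could also be made after the data are seen.

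**Working it through.** **Inputs.** Margin M=0.15, reference (EC) rate 0.25, one-sided alpha 0.05 and power 0.80 (Protocol, Sample size calculation; SAP section 3). Planned size 110 per arm. The documents also cite an expected EC rate of 20-25%, so both ends are used. The documents do not state the true difference. It is assumed to be zero, which is the value that reproduces 104.

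**1. The plan's own figure.** n per arm = [(z_alpha·s0 + z_power·s1)/M]², where s0 uses the rates constrained to differ by -0.15 and s1 uses the true rates.
- Constrained rates: 0.1891 (HnB) and 0.3391 (EC), so s0 = √(0.1891×0.8109 + 0.3391×0.6609) = 0.6143.
- s1 = √(2×0.25×0.75) = 0.6124.
- One-sided 0.05: [(1.645×0.6143 + 0.842×0.6124)/0.15]² = 103.5, rounded up to 104. The plan's figure is reproduced.
- One-sided 0.025: replacing 1.645 by 1.960 gives 131.4.

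So 104 per arm belongs to one-sided 0.05, not to the level implied by the 95% limits.

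**2. Power and type I error under each criterion.** All binomial outcomes at 110 per arm were enumerated and the Farrington-Manning Z computed for each. The sized test passes if Z>1.645. The 95% limit passes if Z>1.960.

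| EC rate | Power, p<0.05 decides | Power, 95% limit decides | Disagree | Type I error, p<0.05 | Type I error, 95% limit |
|---|---|---|---|---|---|
| 25% | 82.5% | 72.8% | 9.7% | 4.97% | 2.43% |
| 20% | 87.1% | 79.1% | 8.0% | 4.79% | 2.40% |

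Power assumes equal true rates. Type I error is at a true difference of -0.15 (HnB 10% against EC 25%, and HnB 5% against EC 20%). Every pass by the 95% limit is also a pass by p<0.05, so disagreement is the difference in power: 0.8249-0.7279=0.0970 and 0.8706-0.7911=0.0795.

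**3. At the approved ITT size of 217 (SAP 9.7).** The split by arm is not given in the text. For splits from 110/107 to 107/110, power is 81.7-82.0% against 72.3-72.9% (EC 25%), and 86.5-86.7% against 78.2-79.0% (EC 20%).

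**4. What the table would show at 110 per arm.** With 28 EC and 22 HnB quitters the difference is 22/110-28/110 = -0.0545. The Farrington-Manning standard error is 0.0565, so Z = (-0.0545+0.15)/0.0565 = 1.689. Lower limits come from inverting the score.

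| EC | HnB | One-sided p | 90% lower limit | 95% lower limit |
|---|---|---|---|---|
| 28 | 22 | 0.0456 | -0.1475 | -0.165 |
| 28 | 23 | 0.0332 | -0.139 | -0.157 |
| 28 | 24 | 0.0238 | -0.131 | -0.149 |
| 22 | 15 | 0.0455 | -0.148 | -0.164 |

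The first, second and fourth rows split the two criteria. In the third row both pass.

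**5. Which 90% limit matches the test.** Over 1,400 possible tables at 110 per arm, p<0.05 and a 90% score lower limit above -0.15 agreed every time. An unpooled Wald 90% limit disagrees with the test in 0.04% (EC 25%) to 0.42% (EC 20%) of trials, so the rule should name the score-based limit.

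**6. The 10-15% wording.** With a margin of 0.10 at one-sided 0.05, the formula in step 1 gives 232.4 (EC 25%) and 200.1 (EC 20%) per arm. The figure of 104 follows from 15% only.

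**The case against.** The strongest reply is that the rule can already be reconstructed. SAP section 3 gives the test, direction, alpha and margin. SAP 7.1 names the same test and threshold, and Table E.1b shows one-sided hypotheses and a one-sided p-value. The only alpha in either document is 0.05. The 95% label sits in a mock shell, and 95% is the SAP's usual reporting level across its tables, so it may be purely descriptive. This largely stands, and it is why one-sided p<0.05 is the natural reading. It does not remove the problem: alpha appears only as a sample-size assumption, no sentence carries it to the analysis, and a different level is printed beside the margin.

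A reader might infer that the trial is underpowered at about 73-79%. The documents do not support that, because no section makes the 95% limit decisive. A reader might also infer that type I error is inflated. It is not, because the 95% limit is the stricter criterion.

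A reader might further infer that the primary population is left open because Table E.1b is run for both ITT and PP. The protocol's primary-endpoint section and SAP section 5 ("The quit rates will be evaluated on an intention-to-treat basis") place the primary analysis on an intention-to-treat basis, so it is not open, although SAP 7.1 does not repeat this. The documents do not rank the per-protocol result further, and nothing here requires them to.

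**Conclusion.** The point holds as a mismatch between the sized test and the interval printed beside the margin, together with a missing decision rule in SAP 7.1. The test itself is valid and the sample size is correct for it. Under the natural reading, power meets the plan and type I error is about 5%. The exposure is that the primary table can support opposite conclusions in 8-10% of trials. Power would fall to about 73% (EC 25%) to 79% (EC 20%) only if the 95% limit were taken to decide. The power and disagreement figures rest on equal true quit rates, an EC rate of 20-25% and 110 per arm. They change little at the approved ITT size. This should be fixed, because it concerns the primary conclusion and the correction costs almost nothing.

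**What to change.** In SAP 7.1, state that non-inferiority is concluded in the primary intention-to-treat analysis if the one-sided Farrington-Manning p-value is below 0.05. Add that this is equivalent to the lower limit of the score-based two-sided 90% interval for HnB minus EC exceeding -0.15. In Table E.1b, print those 90% limits beside the margin and mark any 95% limits as descriptive.

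If the 95% limit is meant to decide, say so instead, and restate power at 110 per arm as about 73% (EC 25%) to 79% (EC 20%).

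As a minor consistency correction, replace 10-15% with 15% in the protocol's hypothesis and subject-population paragraphs and in SAP section 3.

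The cost is one or two sentences in SAP 7.1, one relabelled interval in Table E.1b, and a wording change in three places, two of them in the protocol. The data, the test and the sample size do not change. Only the alternative rule would make the stated power less favourable.
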